2.2.1.4 Sensitivity Analysis: Missing Values

Some infants in the FAS are expected to drop out of the study or, for some other reason, not to have a ranking. As described in Section 2.2.1.3, multiple imputation will be used to include these infants in the analysis of the primary and key secondary endpoint.

The following sensitivity analyses will be conducted on the primary and key secondary endpoint to explore the effect of these missing values:

- Worst reasonable case analysis: Infants in an NTRA-2112 group with a missing rank will be assigned the median rank in the placebo group and infants in the placebo group with a missing rank will be assigned the median rank in the combined NTRA-2112 groups. The van Elteren test, stratified by gestation age group and region (North America, Europe, and Israel) will be performed.
- **Best reasonable case analysis**: Infants in an NTRA-2112 group with a missing rank will be assigned the median rank in the respective NTRA-2112 group and infants in the placebo group with a missing rank will be assigned the median rank in the

Confidential Page 25 of 40

placebo group. The van Elteren test, stratified by gestation age group and region (North America, Europe, and Israel) will be performed.

Tipping point analysis: Infants in either of the NTRA-2112 groups with a missing rank will be assigned varying ranks to find the point at which statistical significance is lost. Specifically, if the outcome of the hypothesis test is in favor of a NTRA-2112 group over the placebo group (P-value <0.05), then one day will be added to each of the imputed values for the NTRA-2112 group in each copy of the imputed dataset, whilst the data for the placebo group will remain the same. The 5 imputed datasets will then be combined to run the van Elteren test results using PROC MI procedure in SAS. This "day shifting" will be repeated with one extra day at a time until the outcome of the hypothesis test is no longer in favor of the NTRA-2112 group over the placebo group (i.e. the P-value becomes greater than 0.05). As the overall ranks of NTRA-2112 group increase as the results of adding one day each time to each imputed missing rank, the highest rank for the imputed missing ranks will be truncated at Day 30 (implying that a missing data point is as bad as a death).

• Survival ("time-to-event") analysis: a stratified log rank test will be performed to compare time-to-FEF (the first day of Full External Feeding). In this analysis, infants who experience NEC will be assigned censoring times of 29 days and infants who die will be assigned censoring times of 30 days. Any other infants who withdraw from the study early will be considered censored at the day of their last participation in the study (unless they have already achieved FEF in which case they will not be censored).

This time to event analysis will be reported for the time to FEF as the *first* of 3 consecutive days and again as the *third* of 3 consecutive days of enteral feeding.

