1.3.3 Sample Size and Statistical Power Considerations

Presentation of sample size is based on the hypothesis that NFE in either treatment group is shorter than in the placebo group. Based on limited historical data (Phase 2), the

Confidential Page 14 of 40

conservative mean is 8.0 days for the placebo group and 6.6 days for each of the 2 active dose groups. This assumes a standard deviation of 3.5 days for each group.

The analysis will be based on a nonparametric test. The NFEs for each infant in the FAS will be ranked from shortest time (the best outcome) to longest time. Infants who do not achieve full enteral feeding and also experience necrotizing enterocolitis (NEC) will be assigned the next set of ranks; all the infants experiencing NEC will be ranked in terms of their time to NEC (the earlier the worse) and will be assigned ranks one greater than the rank of the longest time to achieve NFEs. All infants who do not achieve full enteral feeding and die will be assigned the next set of ranks, again with the earliest deaths assigned the largest (i.e. worst) rank. Thus, each infant who has achieved EN or who has died or suffered NEC will have a recorded rank.

Randomization will be stratified by center and by gestational age group. The statistical analysis will stratify the infants by gestational age group and region (North America, Europe, and Israel), but not by center. Because the analysis will be based on ranks, a van Elteren test will be used to compare NTRA-2112 to placebo. To calculate sample size, an independent groups t-test for 85% power to account for the reduced power of the non-parametric test was used (i.e., expect that a t-test with 85% power to have at least 80% power when the van Elteren test is applied). A two-side 5% test will be used to compare each active dose to placebo. These calculations give N = 115 infants per group. To account for the reduction in power caused by potential missing data, the sample size was increased to 130 per group or a total sample size of 390

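### SAP 2.2.1.4 names one median per arm but tests within gestational-age group, so under one drop-out pattern the worst reasonable case can look better than complete cases

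*SAP*

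**What the plan says.** SAP 1.3.3 forms a single ranking: "The NFEs for each infant in the FAS will be ranked from shortest time (the best outcome) to longest time". SAP 2.2.1.4 then defines two reasonable-case analyses for infants without a rank.

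- Worst case: "Infants in an NTRA-2112 group with a missing rank will be assigned the median rank in the placebo group". A missing placebo infant takes the median of the two NTRA-2112 groups combined.
- Best case: each missing infant takes the median of its own treatment group.

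Both apply to the primary endpoint (NFE, days to full enteral feeding) and the key secondary endpoint (NRD, days to discharge or readiness for it). In each, "The van Elteren test, stratified by gestation age group and region (North America, Europe, and Israel) will be performed". Protocol 12.4.9 gives the same assignment rules. Protocol 12.1.1 defines the GA groups as 26+0 to 28+6 and 29+0 to 32+0 weeks.

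No stratum is named for the median, so the plain reading is one value per arm. The text does not expressly exclude within-stratum medians.

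**The concern.** The van Elteren test compares infants only with others in the same GA group and region. A value typical of a whole arm need not be typical of a stratum. If younger infants feed later, the arm-wide placebo median is a favourable score among infants of 26-28 weeks and an unfavourable one among infants of 29-32 weeks.

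The worst reasonable case is meant to lean against the drug. If most missing NTRA-2112 infants are in the younger group, with few missing younger placebo infants to offset them, the rule can lean the other way. It could then give false reassurance when drop-out is uneven between arms and related to prognosis, which is when such a check is most needed.

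**Working it through.** **Design base.** SAP 1.3.3 states: "A two-side 5% test will be used to compare each active dose to placebo"; "an independent groups t-test for 85% power to account for the reduced power of the non-parametric test was used"; "conservative mean is 8.0 days for the placebo group and 6.6 days for each of the 2 active dose groups". It takes the SD as 3.5 days in every arm. With the normal formula, n = 2 × (1.960 + 1.036)² × (3.5/1.4)² = 2 × 8.98 × 6.25 = 112.2, so 113 per group; the exact t calculation gives 114. The SAP says "These calculations give N = 115 infants per group", so its figure reproduces closely. Enrolling 130 for 115 evaluable allows 15 missing per arm, or 15/130 = 11.5%.

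**Assumptions not in the documents.** Share of younger infants 40% (30-50%); difference in mean NFE between GA groups 3 days (2-4); the missingness patterns below. NFE is gamma distributed in whole days with total SD 3.5. With gap D, the placebo means are 8 + 0.6D and 8 − 0.4D. At D = 3 these are 9.8 and 6.8, and 0.4 × 9.8 + 0.6 × 6.8 = 8.0, as planned. NEC and death ranks were not simulated.

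**Where the arm-wide placebo median falls.** At a 40% share and gaps of 2, 3 and 4 days, it lies at the 35th, 27th and 18th percentiles of younger placebo infants (continuous NFE; the whole-day version gives the 40th, 32nd and 21st). So it is better than typical there. Among older NTRA-2112 infants it lies at the 75th, 79th and 84th percentiles, so it is worse than typical.

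**Pass rates, two GA strata.** 130 per arm, true effect 0.7 days, about 1,500 trials per setting. The standard error near 53% is √(0.53 × 0.47/1500) = 1.3 points. Entries are for gaps of 2 / 3 / 4 days.

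| Missing NTRA-2112 v placebo | Plan, worst case | Complete cases | Within-GA median |
|---|---|---|---|
| 15 v 5, all younger | 41 / 53 / 68% | 41 / 44 / 52% | 29 / 33 / 38% |
| 15 v 5, two-thirds younger | 37 / 45 / 54% | 42 / 45 / 51% | not run |
| 15 v 5, proportional to stratum size | 30 / 34 / 40% | 42 / 45 / 54% | 30 / 34 / 40% |
| 7 v 6, all younger (about 5% drop-out) | 36 / 40 / 48% | 43 / 46 / 54% | not run |

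Repeat runs of the first row at a 3-day gap gave 53-54%, 42-44% and 31-33%. That row means 15 of 52 younger NTRA-2112 infants missing (29%) against 5 of 52 younger placebo infants (10%), and no older infant missing. With no true effect, the same pattern gave one-sided false passes of 3.6-4.4% under the plan and 1.6-1.7% with within-GA medians; nominal is 2.5%. With 15 missing in both arms, plan and within-GA medians differed by about 2 to 5 points at the 0.7-day effect; where they differed by 5, the plan was the stricter (17% v 22%).

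**At the planned 1.4-day effect** (mean z, as magnitudes favouring NTRA-2112; all missing infants younger):

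- 15 v 5, 3-day gap: plan 3.53-3.60, complete cases 3.53-3.62, within-GA 3.11-3.13.
- 15 v 5, 2-day gap: plan 3.27, complete cases 3.45.
- 15 v 0, 3-day gap: plan 4.11, complete cases 3.66, within-GA 3.38.

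**Six strata (2 GA × 3 regions), three arms of 130, effect 1.4 days:**

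- Missing only among younger NTRA-2112 infants (28.75% of them; 0.40 × 28.75% = 11.5% of the arm): plan 3.61 v complete cases 3.40 at a 2-day gap, and 4.56 v 3.87 at 4 days. The plan exceeds complete cases in 85% and 100% of trials; within-GA medians do so in 6% and 4%.
- Younger missing 30% NTRA-2112 v 5% placebo, older 5%: exceeds in 24-28% (2 days) and 65-69% (4 days). At 25% v 15%: 3-5% and 9-16%.
- Missing in NTRA-2112 only, over both GA groups: 3.08 v 3.37 and 3.48 v 3.82; exceeds in 7-10%.
- 11.5% missing in every cell: 2.65 v 3.38 and 2.98 v 3.76; exceeds in 1-2%.
- Missing concentrated in younger placebo infants, 2-day gap: 2.59 v 3.36, so the rule is too harsh.

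**The case against.** The strongest reply is that the reversal is a corner case. It needs missing NTRA-2112 infants to be mostly younger and a marked imbalance between arms, and the documents give no reason to expect either. Infants who develop NEC or die without reaching full feeding are not missing: SAP 1.3.3 and 2.2.1.3.2 give them the worst ranks. Under Protocol 9.5.1, infants withdrawn for an event in the first 28 days are still followed if consent stands. What remains is mainly loss of consent and similar drop-out, with no stated link to GA or arm. This stands, and it limits the point.

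A reader might infer that the worst reasonable case is generally too lenient. The results do not support that: in balanced and proportional patterns it is conservative. A reader might also infer that the plan stratifies by GA because younger infants feed later. Protocol 12.1.1 gives no reason. The direction is plausible from Protocol 5.1 and Appendix E, which describe greater feeding difficulty and more complications in smaller or earlier-born infants, but there is no figure.

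Nor does a favourable result here leave the trial without a stringent check. The tipping-point analysis in the same section adds days to imputed NTRA-2112 values only, up to Day 30, and leaves placebo unchanged. The detail of the multiple imputation is not visible in the public text, so nothing is inferred about it.

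What survives is the mismatch itself: the median is stated per arm, the test is run per stratum, and no other section reconciles them.

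**Conclusion.** The point holds in conditional form. Read plainly, the rule feeds an arm-wide value into a within-stratum comparison. The worst reasonable case can exceed complete cases only when missing NTRA-2112 infants are mostly 26-28 weeks and clearly outnumber missing younger placebo infants. In the illustrative 15 v 5 pattern with a 3-day gap, the excess over complete cases is about 10 points of pass rate at a 0.7-day effect, and nil on average at 1.4 days.

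The GA gap, the younger share and the missingness pattern are all assumed. Sizes were worked for the NFE worst case; the best case and NRD share the wording, but their size was not derived. The analysis is supportive: the primary and key secondary tests and the sample size do not depend on it. Low priority.

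**What to change.** In SAP 2.2.1.4, for both reasonable cases, state that a missing infant receives the median NFE (or NRD) of the stated reference group within the infant's own GA group, and within region too where the cell is large enough, falling back to GA group otherwise. Then run the stratified van Elteren test as planned. In every pattern of the six-stratum simulation this kept the worst case below complete cases on average. If within-stratum medians were always intended, the same sentence removes the ambiguity. The cost is one sentence in the SAP and a by-group step in the program; no new data are needed.

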12.4.9. Sensitivity Analysis: Missing Values

The following sensitivity analyses will be conducted on the primary and key secondary endpoints to explore the effect of these missing values:

- Worst reasonable case analysis: Infants in an NTRA-2112 group with a missing rank will be
 assigned the median rank in the placebo group and infants in the placebo group with a missing
 rank will be assigned the median rank in the combined NTRA-2112.
- Best reasonable case analysis: Infants in an NTRA-2112 group with a missing rank will be assigned
 the median rank in the respective NTRA-2112 group and infants in the placebo group with a
 missing rank will be assigned the median rank in the placebo group.
- Tipping point analysis: Infants in any group with a missing rank will be assigned varying ranks to find the point at which the results reverse from favoring one treatment group to the other.
- Survival ("time-to-event") analysis: a log rank test will be performed to compare time-to-FEF. In
 this analysis, infants who experience NEC will be assigned censoring times of 29 days and infants
 who die will be assigned censoring times of 30 days. Any other infants who withdraw from the
 study early will be considered censored at the day of their last participation in the study (unless
 they have already achieved FEF in which case they will not be censored.

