For the futility analysis, the conditional power of showing statistically significant ($P \le 0.05$) evidence of benefit on the primary endpoint at the final analysis will be calculated for each dose group. Conditional power will be calculated from the z-value based on the interim analysis, treating the primary endpoint as a continuous variable, approximately following the normal distribution. The conditional power will be calculated based on the observed interim trend of effect size, not the original expectation in the sample size calculation. If the conditional power is less than 35% in either dose, continuing to enter infants in that dose group will be considered statistically futile.

The futility analysis results, including the calculated conditional power for each dose group and summaries of selected key safety parameters (adverse events, lab tests, physical exams, and vital signs), will be presented to the Data Monitoring Committee, who will review the results and make a final recommendation regarding the continuation or discontinuation of one or both dose arms. The recommendation will be based on the conditional power and the totality of the clinical data available.

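### The worst-reasonable-case analysis gives missing placebo infants the median of both doses combined, so how strict each dose-versus-placebo check is depends on the dose not being compared

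*SAP*

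**What the plan says.** SAP 2.2.1.4 plans several sensitivity analyses for missing ranks on the primary (NFE) and key secondary (NRD) endpoints. Two of them assign medians:

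- **Worst reasonable case, active infants:** "Infants in an NTRA-2112 group with a missing rank will be assigned the median rank in the placebo group".
- **Worst reasonable case, placebo infants:** a missing rank "will be assigned the median rank in the combined NTRA-2112 groups". Protocol 12.4.9 agrees: a missing "rank will be assigned the median rank in the combined NTRA-2112".
- **Best reasonable case, active infants:** a missing rank "will be assigned the median rank in the respective NTRA-2112 group". Placebo infants take the placebo median.

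The confirmatory tests never combine the doses. SAP 1.7 compares the high dose with placebo on the primary and then the key secondary endpoint, and only then the low dose in the same order. SAP 1.3.3 has the same structure: "A two-side 5% test will be used to compare each active dose to placebo". SAP 3.1 lets the monitoring committee recommend "continuation or discontinuation of one or both dose arms", and 2.2.1.4 does not say whether the infants of a stopped dose still count in the combined median.

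**The concern.** In a two-arm comparison, a natural pessimistic scenario gives each arm's missing infants the typical outcome of the other arm. The SAP does this for missing active infants. For missing placebo infants it uses a value that mixes in a third arm. If that third arm is weaker than the tested dose, the mixed median is a longer time, placebo is credited with less, and an analysis labelled as the worst reasonable case is less severe than the label suggests. If the third arm is better, the analysis is more severe. In both cases the result for one dose moves with data that say nothing about that dose against placebo.

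The milder direction is foreseeable. SAP 1.7 justifies testing the high dose first by saying that it may do better than the low dose. If so, the softening falls on the high-dose comparison, which gates every later test. The stake is how far a reader can trust the robustness statement attached to that result.

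**Working it through.** **Inputs from the documents.** Means: "conservative mean is 8.0 days for the placebo group and 6.6 days for each of the 2 active dose groups". Spread: "This assumes a standard deviation of 3.5 days for each group". Two-sided alpha 0.05, 85% t-test power, 115 per group raised to 130 (SAP 1.3.3). Dropout 5% at sample size re-estimation, and a futility look at 150 or more randomised (SAP 3.1), which is about 50 per arm at 1:1:1.

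**The plan's own figure.** n = 2(z₀.₉₇₅ + z₀.₈₅)²σ²/δ² = 2 × (1.960 + 1.036)² × 3.5²/1.4² = 112.2, so 113 per group. The exact t-test gives 113.2, so 114. The stated 115 is close enough. The rise to 130 implies 1 − 115/130 = 11.5% missing. The documents give no pass rate for the worst-case analysis, so there is nothing further to reproduce.

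**How far the assigned value moves.** Take a tested dose at 6.6 days and the other dose at the placebo mean of 8.0. With normal days and two full arms, the combined median is the midpoint, (6.6 + 8.0)/2 = 7.3; the simulated value is 7.2. If the other arm stopped at 50, it is close to the weighted mean, (130 × 6.6 + 50 × 8.0)/180 = 6.99; simulated 7.0. The tested dose's own median is 6.6.

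**Effect on the check.** 4,000 simulated trials per scenario; 130 per arm unless stopped; data missing completely at random at the same rate in each arm; days rounded; single-stratum Wilcoxon test. A pass is two-sided P<0.05 in favour of the dose. Each simulated trial was tested both ways. The tested dose is at 6.6 days and placebo at 8.0.

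| Other dose (assumed) | Missing | Days | Combined median | Own-dose median | Difference (points) |
|---|---|---|---|---|---|
| 8.0, full arm | 11.5% | normal | 74.2% | 64.2% | +10.0 |
| 8.0, full arm | 11.5% | gamma | 87.0% | 76.4% | +10.6 |
| 8.0, stopped at 50 | 11.5% | normal | 69.5% | 63.5% | +6.0 |
| 8.0, stopped at 50 | 11.5% | gamma | 81.9% | 75.5% | +6.4 |
| 7.3, full arm | 11.5% | gamma | 79.8% | 75.7% | +4.1 |
| 8.0, full arm | 5% | normal | 84.6% | 82.5% | +2.1 |
| 8.0, full arm | 5% | gamma | 91.7% | 90.0% | +1.7 |
| 6.6, full arm | 11.5% | normal | 63.1% | 62.9% | +0.2 |
| 6.6, stopped at 50 | 11.5% | normal | 63.8% | 63.6% | +0.2 |
| 5.5, full arm | 11.5% | gamma | 66.5% | 76.0% | −9.5 |

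Separately programmed gamma simulations of the second row gave 83% v 75% and 88% v 77%, hence a range of 8 to 11 points.

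For scale, in the first row an analysis of observed infants only passes in 83.7% of trials. The own-dose swap costs 83.7 − 64.2 = 19.5 points; the combined median costs 83.7 − 74.2 = 9.5. About half of the intended severity is lost in that scenario.

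**Low dose tested.** With the low dose at 7.3 and the high dose at 6.6 (normal days, 11.5% missing), the check passes in 12.6% of trials with the combined median and 14.0% with the low dose's own, so here pooling makes it slightly harder.

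**The case against.** The case for leaving the rule alone has force, and several stronger readings that a reader might infer are not supported.

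- **That stopping a dose softens the check.** It does not. An equally effective dose stopped at 50 infants changes nothing (63.8% v 63.6%). Only a weaker arm matters, and a stopped weak arm dilutes less than a full one.
- **That both dose comparisons are softened.** The low dose is formally tested only after the high dose has won on both endpoints. In that setting pooling usually has no effect or makes the check harder.
- **That the check passes too often.** The tabulated scenarios have a dose that truly works and data missing at random, so a pass is the right answer and the extra passes are not false positives. With an ineffective tested dose, the check passes in about 2% of trials or fewer. The exception is an other dose assumed worse than placebo (9.4 days): 2.2% to 5.4% at 5% to 20% missing, against 0.2% to 1.5% with the own-dose median. Nothing in the documents suggests such a dose.
- **That a confirmatory claim is at risk.** The primary approach to missing ranks is multiple imputation (SAP 1.6.5). The worst case is exploratory and has no pass/fail rule.

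It is also fair to say that the plan assumes equal effects in the two doses, that 5% is the only dropout rate it states, and that NEC and death receive ranks and so are not missing. A combined median has one merit: each missing placebo infant keeps a single prespecified value in both comparisons.

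What stands is narrower. Strictness depends on an arm outside the comparison, no reason is given, and the best case in the same section avoids it. The tipping-point analysis does not replace this check, because it shifts only the active infants and holds placebo fixed.

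**Conclusion.** The mismatch is real and minor. The combined median makes the worst-case check milder than a swap between the compared arms when the other dose is weaker, chiefly in the high-dose test, and harsher when the other dose is better. With an inert low dose the high-dose check passes about 8 to 11 points more often at 11.5% missing, about 6 points if that arm stopped at about 50 infants, and about 2 points at 5% missing. With equal doses the difference is immaterial. The primary test and its type I error are untouched.

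These sizes rest on assumptions outside the documents: other-dose means of 5.5, 7.3 and 8.0 days, the shape of the day distribution, a stop at 50, and missingness unrelated to outcome. The simulations leave out strata and NEC or death ranks, and assign medians on the day scale, whereas the SAP speaks of ranks. Only NFE was simulated; the same reasoning applies to NRD, but no size is claimed for it.

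**What to change.** In the worst-reasonable-case bullet of SAP 2.2.1.4, replace the reference to the combined NTRA-2112 groups with *the NTRA-2112 group being compared*, for both NFE and NRD. This matches the dose-by-dose tests and the best-case rule, and it removes the question of whether a stopped dose enters the median. Protocol 12.4 gives the SAP precedence on methods, so the SAP edit is enough.

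The cost is a few words, with no new data and no change in sample size. There are two downsides: a missing placebo infant takes a different value in each comparison, and the high-dose sensitivity result may be slightly less favourable.

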2.2.1.3.2 Ranks for NEC and Death of Subjects

Infants who experience NEC (Necrotizing Enterocolitis) will be assigned ranks of NFE according to censoring times of 29 days and infants who die will be assigned ranks of NFE according to censoring times of 30 days. The individual ranks among subjects experiencing NEC and the individual ranks among subjects who die will be handled according to Section 1.3.3.

Since it can take significantly longer than 28 days to be discharged or being ready to be discharged, infants who experience NEC (Necrotizing Enterocolitis) will be assigned ranks of NRD according to censoring times of 181 days and infants who die will be assigned ranks of NRD according to censoring times of 182 days. The individual ranks among subjects experiencing NEC and the individual ranks among subjects who die will be handled according to Section 1.3.3.

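### The tipping-point analysis caps imputed values at Day 30 for the discharge endpoint too, where death is coded Day 182, so penalising missing NTRA-2112 infants can improve the result

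*SAP*

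**What the plan says.** SAP 2.2.1.4 opens its list with "The following sensitivity analyses will be conducted on the primary and key secondary endpoint to explore the effect of these missing values". The tipping-point bullet in that list carries no restriction to one endpoint. Its rule for an NTRA-2112 dose that beats placebo is that "one day will be added to each of the imputed values for the NTRA-2112 group in each copy of the imputed dataset". Placebo data stay fixed, and the step is repeated one day at a time until significance at 0.05 is lost. The upper limit is stated once: "the highest rank for the imputed missing ranks will be truncated at Day 30". A remark in brackets explains this as treating a missing value like a death.

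SAP 2.2.1.3.2 sets the codes for bad outcomes separately by endpoint. For NFE, NEC is Day 29 and "infants who die will be assigned ranks of NFE according to censoring times of 30 days". For NRD, NEC is Day 181, while "infants who die will be assigned ranks of NRD according to censoring times of 182 days". The reason given is that discharge can take much longer than 28 days. SAP section 4 records that 2.2.1.3.2 was changed to allow up to 180 days for NRD. It lists no corresponding change to the tipping-point ceiling.

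**The concern.** A tipping-point analysis asks how bad the missing infants' outcomes would have to be before the finding disappears. It therefore has to be able to make those outcomes worse, up to the worst value on the scale. For NFE, Day 30 is that value. For NRD, Day 30 lies well inside the range of ordinary discharge times that the SAP anticipates. A ceiling there stops the search far short of the worst outcome. For any infant imputed above 30 it also replaces a later discharge with an earlier one.

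The direct consequence is that the NRD result can fail to tip for reasons unrelated to how the missing infants fared, and that failure would be reported as robustness. NRD at the high dose is step 2 of the hierarchy in SAP 1.7, and the low dose is tested only if it succeeds. The tipping-point analysis itself gates nothing, but it supports the credibility of a result that does.

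**Working it through.** **1. The two sections side by side**

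| | NFE | NRD |
|---|---|---|
| NEC code (SAP 2.2.1.3.2) | 29 | 181 |
| Death code (SAP 2.2.1.3.2) | 30 | 182 |
| Tipping-point ceiling (SAP 2.2.1.4) | 30 | 30 (no other value stated) |
| Death code minus ceiling | 0 | 182 − 30 = 152 days |

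The rule for an imputed value x at shift k is min(x + k, 30). For x = 45 this gives 30 at every k, a 15-day improvement. For x = 20 it gives 21, 22 and so on up to 30. Once every imputed value sits at 30, further steps change nothing.

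**2. Arm size and amount of missing data**

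The inputs come from SAP 1.3.3: means of 8.0 and 6.6 days, SD 3.5, two-sided 5%, 85% power.

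- n per arm = 2 × (1.960 + 1.036)² × 3.5² / 1.4² = 112.2, so 113. The exact t-test gives 113.2, so 114.
- The SAP states 115, within two infants, and raises it to 130. The allowance is 15 of 130, or 11.5%.
- SAP 3.1 uses a 5% dropout rate, which is about 7 of 130.

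Both missing-data figures are used below.

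**3. Illustration for NRD**

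The documents give no NRD mean, SD or effect, so these are assumptions: placebo N(m, 14) and active N(m − 5, 14), rounded to days, with m from 25 to 55. Each setting has 2,000 simulated trials of 130 per arm, with k infants missing on NTRA-2112. The statistic is the tie-corrected Wilcoxon z, and positive favours NTRA-2112. The two ceiling columns are at full shift.

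| Missing | Placebo mean m | Unshifted | Day 30 ceiling | Day 182 ceiling |
|---|---|---|---|---|
| 15 | 25 | 2.72 | 1.96 | 0.80 |
| 15 | 35 | 2.78 | 2.91 | 0.85 |
| 15 | 45 | 2.78 | 3.61 | 0.85 |
| 15 | 55 | 2.78 | 3.95 | 0.85 |
| 7 | 45 | 2.77 | 3.16 | 1.87 |

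With 7 missing at 45 days, the Day 182 ceiling takes the mean z below 1.96, while the Day 30 ceiling moves it the other way. Repeat runs agreed within simulation error.

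**4. A version closer to the SAP's method**

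This used 15 of 130 missing per arm, an assumed effect of 0.4 SD and five imputations drawn from the same arm and gestational-age stratum. The test was van Elteren on two gestational-age strata with pooled z, over 200 trials per setting. Entries are the mean z, with the share of trials still significant in brackets.

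| Placebo mean, SD | Unshifted | Day 30, full shift | Day 182, full shift |
|---|---|---|---|
| 35, 12 | 3.28 (90%) | 3.46 (93%) | 1.44 (25%) |
| 45, 15 | 3.20 (92%) | 3.97 (98%) | 1.38 (24%) |
| 60, 18 | 3.44 (94%) | 4.53 (100%) | 1.56 (32%) |

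The share of trials in which the penalised result was more favourable than the unshifted one, across 7 and 15 missing, was:

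- 45 and 60 days: 100% at every shift checked (+1, +20, +150).
- 35 days: 100% at +1 day and 76–82% at the largest shift.
- 25 days: 68–74% at +1 day and 0% from +20 days.
- 20 days: 0–2%.

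At the short means with 15 missing, trials still significant at full shift were 43% (Day 30) against 28% (Day 182) at 20 days, and 62% against 29% at 25 days. Day 30 was the weaker stress test in every setting.

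**The case against.** The strongest reply is that the ceiling sentence states its own principle: a missing value can be no worse than a death. A statistician applying that principle to NRD would use 182. The list is also loosely worded, since its survival bullet covers only time to full enteral feeding. On this view the fault is an NRD value left unstated. That is a fair account of how the sentence probably arose, but it does not rescue the text. The survival bullet says which endpoint it covers and the tipping-point bullet does not. If Day 30 is read as NFE-only, NRD has no ceiling at all, and shifted values could pass the death code.

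A second reply is that the ceiling is meant to limit increases and never to lower a value. Under that reading the reversal disappears. With 15 missing and a 45-day mean, z goes from 2.79 to 2.73, so the test still barely moves and is uninformative.

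Several limits do stand:

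- The imputation details (SAP 2.2.1.3.1) are not in the public text, so how imputed NRD values are bounded cannot be checked.
- The reversal depends on a large share of imputed NRD values exceeding 30 days.
- With 5% missing the gap between the two ceilings is less than half as large (3.16 − 1.87 = 1.29, against 3.61 − 0.85 = 2.76).
- The analysis is supportive, and NRD also has a worst-reasonable-case analysis and a per-protocol repeat, neither of which uses this ceiling.

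**Conclusion.** The concern holds. SAP 2.2.1.4 and 2.2.1.3.2 contradict each other for NRD: the ceiling said to represent death is 152 days below the value assigned to death. That mismatch rests on the text alone.

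Its effect depends on the NRD distribution, which the documents do not give. At assumed placebo means of 45 days or more, the literal rule makes the result more favourable to NTRA-2112 as missing infants are penalised. At 35 days it usually does. At 20 to 25 days it leaves a real but weaker stress test than Day 182. The SAP's own statement that discharge can run well past 28 days makes the upper part of that range relevant.

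The primary analysis, the NFE tipping-point analysis and the Type I error rate are not affected. This should be corrected before unblinding, because as written the analysis cannot properly stress the key secondary endpoint.

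**What to change.** In the tipping-point bullet of SAP 2.2.1.4, replace the single ceiling with the value assigned to death for the endpoint being analysed: Day 30 for NFE and Day 182 for NRD. Add that a shift may never lower an imputed value. A coarser step for NRD, for example 5 to 7 days, is optional. It shortens the search, but the one-day loop has no step limit and can reach 182 anyway.

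The cost is one sentence in the SAP and one program parameter, with no loss to any other analysis.
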